### 6-Week Cohorts

Trial phase	Target phase day	Analysis time point (numeric version)	Analysis time point b	Time interval (days) a
Screening	$-\infty$	-1	Screening	$<0$
Treatment phase	1	0	Baseline	$\leq 1$
	2	0.2	Day 2	2
	3	0.3	Day 3	[3,5]
	7	1	Week 1	[6,11]
	14	2	Week 2	[12,18]
	21	3	Week 3	[19,25]
	28	4	Week 4	[26,32]
	35	5	Week 5	[33,39]
	42	6	Week 6	[40, $+\infty$ ]
	last visit while on study therapy or 3 days after the day of last dose	999	EOT	
Follow-up phase	25	16	Follow-up Week 4	[1,39]

	53	20	Follow-up Week 8	[40,67]
	81	24	Follow-up Week 12	[68,102]
	123	30	Follow-up Week 18	[103,144]
	165	36	Follow-up Week 24	[145, $+\infty$ ]

## 8-Week Cohorts

Trial phase	Target phase day	Analysis time point (numeric version)	Analysis time point b	Time interval (days) a
Screening	$-\infty$	-1	Screening	$<0$
Treatment phase	1	0	Baseline	$\leq 1$
	2	0.2	Day 2	2
	3	0.3	Day 3	[3,5]
	7	1	Week 1	[6,11]
	14	2	Week 2	[12,18]
	21	3	Week 3	[19,25]
	28	4	Week 4	[26,32]
	35	5	Week 5	[33,39]
	42	6	Week 6	[40,46]
	49	7	Week 7	[47,53]
	56	8	Week 8	[54, $+\infty$ ]
	last visit while on study therapy or 3 days after the day of last dose	999	EOT	
	Follow-up phase	25	16	Follow-up Week 4
53		20	Follow-up Week 8	[40,67]
81		24	Follow-up Week 12	[68,102]
123		30	Follow-up Week 18	[103,144]

	165	36	Follow-up Week 24	[145, +∞]
--	-----	----	-------------------	-----------

**12-Week Cohorts**

Trial phase	Target phase day	Analysis time point (numeric version)	Analysis time point b	Time interval (days) a
Screening	-∞	-1	Screening	<0
Treatment phase	1	0	Baseline	≤1
	2	0.2	Day 2	2
	3	0.3	Day 3	[3,5]
	7	1	Week 1	[6,11]
	14	2	Week 2	[12,18]
	21	3	Week 3	[19,25]
	28	4	Week 4	[26,32]
	35	5	Week 5	[33,39]
	42	6	Week 6	[40,46]
	49	7	Week 7	[47,53]
	56	8	Week 8	[54,60]
	84	12	Week 12	[82, +∞]
		last visit while on study therapy or 3 days after the day of last dose	999	EOT
Follow-up phase	25	16	Follow-up Week 4	[1,39]
	53	20	Follow-up Week 8	[40,67]

	81	24	Follow-up Week 12	[68,102]
	123	30	Follow-up Week 18	[103,144]
	165	36	Follow-up Week 24	[145, +∞]

a The reference day of the Treatment and Screening phase is the day of the first study drug intake (= day 1 in Treatment phase).

b Target day in follow-up phase equals target day in the protocol minus 3 days.

If two visits fall within the same interval, the last measurement within the interval will be used for the descriptive statistics/tabulations per time point and graphics in order to have only one evaluation per subject per analysis time point. If there are two measurements on the same day and time, then the measurement with the highest sequence number will be used. Listings will include all values.

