Secondary Endpoints:	
 The proportion of subjects who have a sustained virologic response (SVR; i.e., HCV RNA concentration below the lower limit of quantitation [$<LLOQ$; <15 IU/mL]) at 4, 8, 12, 18 and 24 weeks after the last actual dose of treatment PK parameters for AL-335 (and metabolites), ODV and SMV in plasma The proportion of subjects who experience virologic relapse during the follow-up period. The proportion of subjects who have on treatment failure while receiving study medication Viral kinetics, as determined at different timepoints during treatment by the proportion of subjects who achieve 
 HCV RNA $<LLOQ$ undetectable HCV RNA $<LLOQ$ Time to achieve undetectable HCV RNA and $<LLOQ$ HCV RNA The amino acid sequence of the NS5A, NS5B and NS3/4A proteins at baseline and post-baseline in subjects who fail treatment Effect of various baseline and host disease-related characteristics on treatment outcome
Duration of Treatment and Study Period:	
Up to 43 weeks (from screening through study completion) for each enrolled subject as follows:
 
 Screening: Up to 50 days Study Period: Up to 12 weeks Follow-up: Up to 24 weeks after completion of study medications
Number of Sites and Location:	Up to 50 sites globally
Sample Size:	Up to 320 treatment-naïve and treatment experienced subjects with CHC infection will be enrolled in up to 16 cohorts. Since this is an exploratory study, no formal sample size calculation has been performed. A total sample size of 10-20 subjects/cohort is considered sufficient to explore the safety, pharmacokinetics, and efficacy of the possible study regimens in various HCV-infected subpopulations (e.g., GT1, compensated cirrhosis, etc).

**Inclusion
Criteria:**

Main Inclusion Criteria for All Subjects:

1. Subject has provided written consent.
2. In the Investigator's opinion, the subject is able to understand and comply with protocol requirements, instructions, and protocol-stated restrictions and is likely to complete the study as planned.
3. Male or female, 18–70 years of age.
4. Body mass index (BMI) 18–35 kg/m², inclusive.
5. A woman of childbearing potential must have a negative serum (β -human chorionic gonadotropin) pregnancy test at screening.
6. Female subjects must either:
 - not be of childbearing potential defined as:

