PK Samples ⁵			X			X	X	X	X
Hematology ⁶		X	X			X	X		X
Serum Chemistries ⁶		X	X			X	X		X
Urinalysis		X	X			X	X		X
ALT/AST ⁶		X	X			X	X	X	X
HCV RNA concentrations ⁷		X	X	X	X	X	X	X	X
Plasma for drug resistance monitoring ⁸			X	X	X	X	X	X	X
Pregnancy Test ⁹		X							X
Optional stored serum sample ¹⁰		X	X			X	X	X	X

⁵ A single predose PK sample will be collected at each indicated visit for AL-335 (and metabolites), ODV and SMV concentrations for all subjects. In addition, PK samples will be collected at Week 3, 2-4 hours postdose, and at Week 4, 6-8 hours postdose. Subjects in the intensive PK subset will have the following samples collected at the Week 2 visit Predose (within 0.5 hour) and 0.5, 1, 2, 3, 4, 6, 9, and 24 hours postdose.

⁶ Blood for routine safety evaluations should be collected in a fasted state.

⁷ Plasma for HCV RNA analysis to be collected predose at Day 1, 2 and 3.

⁸ Plasma collected for HCV RNA resistance monitoring will be collected at the same time as HCV RNA quantification. The Day 1 samples must be collected predose.

⁹ A highly sensitive pregnancy test (e.g., urine or plasma) must be conducted immediately (within 4 days) prior to initiating treatment on Day 1 (local results may be used for this eligibility determination)

¹⁰ For additional safety investigations as needed.

* Weekly visit may occur ± 1 day from the expected visit date.

Table 6-4. Schedule of Events for Post-dosing (Safety and Virology) Follow-up Visits (All Treatment Cohorts)

Post-dosing Follow-up							
Assessment	Early Termination (ET) Visit ¹	Safety Follow-up Visit 4 Weeks (±1 week) After the Last Actual Dose of Study Drug	Virology Follow-up Visits (After end of Treatment ² OR After Time of Treatment Failure [if earlier]) ³				Week 24 (±2 weeks)
			Week 4 (±1 week) ⁴	Week 8 (±1 weeks)	Week 12 (±2 weeks)	Week 18 (±2 weeks)	
Physical Exam ⁵	X	X					
Echocardiogram	X	X					
Vital Signs	X	X					
Triplicate 12 Lead ECG	X	X					
Liver Ultrasound (subjects with cirrhosis)							X
Serum Chemistry w/ ALT & AST	X	X					
Hematology	X	X					
Urinalysis	X	X					
HCV RNA concentration	X	X	X	X	X	X	X
Plasma for drug resistance monitoring	X	X	X	X	X	X	X
AE & Conmed Evaluation	X	X	X	X	X	X	X
PK Samples ⁶	X	X	X	X	X	X	X

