### 3.2 Visit Windows and Phase Definitions

Phases will be constructed as follows:

Trial phase	Start date	End date
Screening (phase 0)	Minimum of Date of signing the informed consent and Date of the first screening visit	1 day before the first study drug intake (AL-335+ODV( $\pm$ SMV))
Treatment (phase 1)	Date of first study drug intake (AL-335+ODV( $\pm$ SMV))	Date of last study drug intake: MAXIMUM{Date of last study drug intake (AL-335+ODV( $\pm$ SMV))} + 3 days*
Follow-up (phase 2)	End date of Treatment phase + 1	Trial termination date

\*In case the last study drug intake is missing, other dates can be used instead for date of last study drug intake: E.g. if the subject discontinued treatment (known from the disposition table): date of the withdrawal visit, if the latter is not available: date of first available FU visit minus the number of days in follow-up at which this FU visit was scheduled according to the protocol. If those dates are not available, date of trial termination.

The number of days in the treatment phase (ADY) will be defined as:

$ADY = \text{visit date} - \text{date of first study drug intake} + 1$  for visits on or after the day of first study drug intake

$ADY = \text{visit date} - \text{date of first study drug intake}$  for visits before the day of first study drug intake

In case the date of first study drug intake is missing, the date of the baseline visit can be used as date of first study drug.

Actual End of Treatment visit (EOT) is defined as the last visit in the Treatment phase.

All visits (regardless the investigated parameter) will be allocated within each phase to analysis time points based on the number of days in phase (ADY):

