**Otherwise SVR12 is classified as a failure (0).**

\* Confirmed means that the criterion should be fulfilled at 2 or more consecutive time points or at the last observed time point.

Time point of SVR12:

- 12 weeks after the actual EOT (i.e. the last available measurement in the SVR12 analysis window)
- or, if not available, the first available measurement at least 12 weeks after the actual EOT (i.e. the first available measurement after the SVR12 analysis window)
- or, if not available (i.e. no measurement at least 12 weeks after the actual EOT), the subject is considered a failure.

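### The SAP's Follow-up Week 12 window opens one day after the protocol's, so a compliant day-70 sample cannot be used for SVR12

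*SAP*

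**What the plan says.** **Protocol.** The follow-up schedule (Table 6-4, Section 6.1) lists the virology visit as "Week 12 (±2 weeks" and dates the virology visits from end of treatment, or from treatment failure if earlier. The secondary endpoints (Section 3.2.2) time SVR "at 4, 8, 12, 18 and 24 weeks after the last actual dose of treatment". The Definitions list equates end of treatment with completing or prematurely stopping dosing.

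**SAP 3.2.** The Treatment phase ends three days after the last study drug intake, and Follow-up begins at "End date of Treatment phase + 1". Every visit is placed in an analysis window by its day number within the phase, not by its nominal label. The footnote to the tables says "Target day in follow-up phase equals target day in the protocol minus 3 days". The 6-, 8- and 12-week tables share the same follow-up rows, including "Follow-up Week 8 [40,67"] and "Follow-up Week 12 [68,102"].

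**SAP 9.2.1.** SVR12 uses the last measurement in its own window. Failing that, it uses "if not available, the first available measurement at least 12 weeks after the actual EOT", which the SAP explains as the first one after the window. If there is none, the subject is a failure.

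**The concern.** An analysis window for the primary efficacy endpoint should contain every day on which the protocol lets the visit take place. Here the first permitted Week 12 day falls just outside. Allocation goes by day count, so the sample is filed under Week 8, and the SVR12 rule looks only inside its window or after it. The subject attended on time, yet for SVR12 the visit is treated as missing.

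Two consequences can follow:

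- SVR12 is read from a later sample, nominally Week 18, so a late relapse would count against the 12-week endpoint.
- With no later sample at all, a subject with an on-time result below LLOQ is reported as a failure.

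Cohorts hold 10 to 20 subjects, so a single changed outcome is visible in the cohort result.

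**Working it through.** **Inputs**
- Protocol visit windows (Table 6-4): Week 4 ±1 week, Week 8 ±1, Week 12 ±2, Week 18 ±2, Week 24 ±2.
- SAP 3.2: Treatment phase ends at last dose + 3 days; Follow-up day 1 is the next day.
- SAP 3.2 follow-up targets 25, 53, 81, 123, 165, with upper limits 39, 67, 102, 144 and the last window open-ended.

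**Step 1: day count.** SAP 3.2 writes out a day formula only from first drug intake. For follow-up the offset comes from the phase dates. Follow-up day 1 is last dose + 4, so follow-up day = days since last dose − 3.

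**Step 2: reproduce the SAP's figures.**
- Targets: 28, 56, 84, 126, 168 minus 3 gives 25, 53, 81, 123, 165, as stated. Offsets of 2 or 4 do not give these targets.
- Cut-points: (25+53)/2 = 39; (53+81)/2 = 67; (81+123)/2 = 102; (123+165)/2 = 144. These are the stated upper limits, so each midpoint day goes to the earlier visit.

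**Step 3: map the permitted visit days.**

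| Visit | Days since last dose | Follow-up days | SAP window | Fits? |
|---|---|---|---|---|
| Week 4 | 21–35 | 18–32 | [1,39] | yes |
| Week 8 | 49–63 | 46–60 | [40,67] | yes |
| Week 12 | 70–98 | 67–95 | [68,102] | all but day 67 |
| Week 18 | 112–140 | 109–137 | [103,144] | yes |
| Week 24 | 154–182 | 151–179 | [145,∞) | yes |

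Day 70 after last dose (follow-up day 67) is the only permitted day in the schedule that lands in another visit's window. It is 14 days from both the Week 8 target (70 − 56) and the Week 12 target (84 − 70).

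**Step 4: follow the SVR12 rule for a day-70 sample.** The SVR12 window [68,102] is days 71 to 105 after last dose. With no other HCV RNA sample in that span, the first choice is empty. The fallback takes the first sample after the window: Week 18, Week 24 if Week 18 was missed, or an unscheduled retest. With none, the result is failure.

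**Step 5: size.**
- Permitted Week 12 days: 98 − 70 + 1 = 29. Share affected: 1/29 = 3.4%.
- Misfiled samples per 20 subjects with uniform visit dates: 20/29 = 0.69.
- False failures also need no later sample. The documents give no such rate. Assuming 2% to 10%, 0.69 × 0.02 = 0.014 and 0.69 × 0.10 = 0.07 per 20 subjects.
- Conditional worst case (Clopper-Pearson 95% CI): 20/20 (83.2% to 100%) would become 19/20 (75.1% to 99.9%).

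**The case against.** **It is a convention, not a slip.** The cut-points are exact midpoints with a consistent tie rule, and nothing in the documents requires analysis windows to contain every permitted visit day. This stands: a reader might infer a calculation error, and there is none. The difficulty is that the tie goes to Week 8, whose permitted window closed at follow-up day 60, and away from the visit for which the protocol allows that day.

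**The anchor is inferred.** Table 6-4 dates the virology visits from end of treatment, and SAP 3.2 defines the EOT visit as the last visit in the Treatment phase, which may be up to three days after the last dose. If a site counts from an EOT visit held k days after last dose (k = 1 to 3), its earliest Week 12 visit is follow-up day 67 + k, at least 68, and the conflict vanishes. This stands as a condition. The protocol's EOT definition and its endpoint wording favor counting from last dose.

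**The harm is remote.** A later sample below LLOQ still gives success. Even a later value at or above LLOQ can be a success if it is unconfirmed and the next is below LLOQ. Protocol Table 1-1 shows Cohorts 1, 2 and 3 each at 20/20 for SVR24; if those are observed Week 24 results, this boundary cannot make any of those 60 subjects a failure. This stands. A reader might take 20/20 falling to 19/20 as the expected effect, but the documents do not support that.

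**The Week 8 value is displaced too.** A reader might infer damage to a Week 8 endpoint, since the last measurement in an interval is the one tabulated. But SVR8 is not among the secondary efficacy endpoints listed in SAP 9.3, and listings keep all values.

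**Conclusion.** The point holds as a minor misalignment. Counting from last dose, the SAP excludes one protocol-compliant day, day 70, from the window for its primary efficacy endpoint, and no rule in SAP 9.2.1 recovers that sample.

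The affected share is 1 of 29 permitted days: about 0.7 samples per 20 subjects under uniform visit dates, fewer if visits cluster near day 84. A misfiled sample is not a changed outcome, and a false failure is much rarer still.

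The conclusion assumes that sites count from last dose, that no other HCV RNA sample falls on days 71 to 105, and that the SVR12 analysis window means the Follow-up Week 12 window of SAP 3.2, the only candidate. The study is exploratory with no significance testing, so no formal inference is at risk.

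**What to change.** In all three tables of SAP 3.2, set Follow-up Week 8 to [40,66] and Follow-up Week 12 to [67,102]. Week 12 then covers days 70 to 105 after last dose, and every permitted follow-up day maps to its own visit. No permitted Week 8 day (follow-up days 46 to 60) moves.

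The cost is two numbers in each of three tables, plus a small loss of uniformity: the midpoint tie rule is broken at this one boundary, and a sample exactly 10 weeks after last dose counts as SVR12. That is one day earlier than the SAP now accepts, since day 71 already qualifies. The last fallback for SVR24 also reads the Week 12 window, so it would see the same sample.

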#### 4. Statistical considerations

Efficacy and safety data will be analysed using SAS® software version 9.4 (SAS institute Inc. ██████ USA).

Pharmacokinetic data from the PK substudy will be analysed using Phoenix® WinNonLin® version 6.4 (Pharsight) and SAS® software version 9.4 (SAS Institute Inc. ██████ USA) for final analysis.

Descriptive statistics will be supplied according to the nature of the criteria:

- Quantitative variable: sample size, arithmetic mean, standard deviation (SD), standard error of the mean (SEM), minimum, median and maximum, and quartiles if necessary (with geometric mean, arithmetic and geometric coefficients of variation (CV), and quartiles for PK parameters, geometric mean will not be reported in case of value equal to 0).
- Qualitative variable: sample size, absolute and relative frequencies per class. Percentages will be provided with one decimal place.

Safety data will be organized by cohort.

All safety and pharmacokinetics listings will be sorted by cohort, subject, and measurement time if applicable.

For all except pharmacokinetics data, cohorts that evaluate the same treatment regimen for the same duration (e.g., Cohort 1b and the first 5 subjects in Cohort 4) will be pooled (using Label “Cohort 1b+Cohort 4 (8 Weeks).” If multiple treatment durations and/or regimens were assessed in a single cohort, the data for that cohort will be presented separately (e.g. Cohort 4 (12 weeks) will be separate from Cohort 4 (8 weeks), which will be pooled with cohort 1b). For cohorts with different clinical characteristics (e.g. HCV genotype, cirrhosis status),

treatment regimens or same treatment regimen but with different durations, data will be presented separately.

For pharmacokinetic data, cohorts that evaluate the same treatment regimen (including study medications and doses) in the same population (cirrhotic vs non-cirrhotic), whatever the duration, or HCV genotype will be pooled, i.e. the presentation of cohorts will be:

- Cohort 1,
- Cohort 1b+4,
- Cohort 2+Cohort 3+Cohort 5,
- Cohort 6.
- Cohort 7+Cohort 8+Cohort 9+Cohort 10+Cohort 11+Cohort 12

#### **Handling of missing and retest values**

No management of missing data will be done, except for pharmacokinetic values (see [section 7.1](#)) and missing or incomplete start/stop dates (see below).

Missing start or end dates for events not aligned to a specific visit/week such as adverse events, medications reported, etc., will be imputed using the following rules:

- A completely missing start date of an event will be set to the date of the first dose of study medication, unless it is clearly indicated that this is an event happening pretreatment. In this case, it will be set to the day before the first dose of study medication.
- A completely missing stop date will not be imputed, but the event will be assumed to be ongoing.
- Partially missing dates where the year is known will be set to 01 January of that year or the first dose of study medication date, if the first dose of study medication occurred in that year.
- Partially missing dates where the year and month are known will be set to the first day of that month or the first dose of study medication date, if the first dose of study medication occurred in that month.

If, by applying the above rules, the stop date is imputed before the start date, then the stop date will be set to be the same as the start date.

For all parameters and for subjects with retest values, the last reliable value will be used as a measurement time before the first investigational medicinal product (IMP) administration (provided it was measured before IMP administration) and the first reliable value will be used as a measurement time after the first IMP administration.

#### **Baseline definition**

For all parameters, baseline will be defined as the last available (and reliable if applicable) single measurement prior to the first IMP administration unless otherwise specified (e.g. ECG).

**Duration**

Duration (in days, hh:mm) will be calculated as the difference between start and stop date and time (e.g. duration of AE (days, hh:mm) = date of AE end date and time – date of AE onset date and time).

Duration (in days) will be calculated as the difference between start and stop date + 1 (e.g. duration of a medication (days) = date of medication end date – date of medication onset date + 1).

**Type I error rate**

No significance testing will be performed. However, two-sided Clopper-Pearson 95% CI will be constructed around the proportion of subjects with sustained virologic response (SVRx) and other virologic response parameters, for each cohort.

**5. Description of study subjects****5.1 Definition of analysis sets**

The following analysis sets will be defined:

Included set (IS): all the subjects included in the study.

Safety/Efficacy/Intent-to-treat population (Safety set): All subjects enrolled into the study who have received at least one dose of any study drug, whether prematurely withdrawn from the study or not, will be included in the safety/efficacy/Intent-to-treat set.

Pharmacokinetic set (PKS): Will be comprised of all safety set subjects except those that they significantly violate the inclusion or exclusion criteria, deviate significantly from the protocol or if data are unavailable or incomplete which may influence the PK analysis. Excluded cases will be documented together with the reason for exclusion.

Per Protocol set (PPS): A per protocol analysis including all subjects enrolled and adherent to the protocol may be performed for certain efficacy analyses.

A subset of major protocol deviations, that may have an impact on the results of the analysis, will be identified prior to database lock. If there are a substantial number of subjects with such protocol deviations, a per-protocol analysis will be performed on the primary endpoint, based on subjects from the Safety set, excluding these subjects. Additional efficacy analysis using the PPS may be performed on an ad-hoc basis.

**5.2 Subject disposition**

A summary table with the description of the number of included subjects, the number of subjects who completed study and the number of subjects who discontinued classified by main reason of withdrawal will be performed by cohort and overall on the subjects included in the Included set. Corresponding individual listings will be provided.

A summary table with the description of the number and percentage of subjects in each analysis set (Safety set, and Pharmacokinetic set) will be performed by cohort and overall. A specific listing of subjects excluded from safety/efficacy and pharmacokinetic analyses will be provided with reason for exclusion.

A summary table with the number and percentage of subjects at each visit will be performed by cohort and overall on the subjects included in the safety set.

Listings with end of study status and study visit dates will also be carried out.

